Primary Endpoints	Efficacy endpoint: Comparison of pre-treatment- and 12-week post-final treatment photographs to assess visible changes in the abdomen.
	Safety endpoint: Incidence of unanticipated adverse device effects (UADE). It is expected there will be zero UADEs.
Secondary Endpoints	The secondary endpoints in the study are:
	
1. Reduction in abdominal circumference as measured by 3-Dimensional imaging.2. Subject- graded Global Aesthetic Improvement Scale at 12-week post-final treatment follow-up.
Sponsor	ZELTIQ Aesthetics, an Allergan affiliate [name] [name], CA 94588

ZELTIQ P/N: [REDACTED]
Protocol Number: ZAT8-003

1. Introduction

1.1 *Background*

Fat reduction and body contouring procedures, which include invasive, minimally-invasive, and non-invasive procedures, have become increasingly popular aesthetic procedures.

Patients who are obese and do not have specific fat bulges but require significant fat reduction to achieve aesthetic results are candidates for invasive and minimally-invasive procedures, such as liposuction and laser-assisted liposuction. Although effective at reducing fat, these invasive and minimally-invasive procedures involve significant patient discomfort, expense, downtime, and the risks typically associated with surgical procedures. As a result, patients who do not require significant fat reduction to achieve meaningful aesthetic results typically seek non-invasive fat reduction and body contouring procedures to avoid the pain, expense, downtime, and surgical risks associated with invasive and minimally-invasive procedures.

ZELTIQ Aesthetics has developed and commercialized a technology for cold-assisted lipolysis. The ZELTIQ CoolSculpting technology is based on the sensitivity of fat cells to cold injury in order to selectively eliminate subcutaneous fat tissue without affecting the skin or other surrounding tissues. The technology, cryolipolysis, enables a non-invasive alternative for subcutaneous fat reduction through cellular apoptosis. The ZELTIQ CoolSculpting System is cleared for use in the United States for the indication of cold-assisted lipolysis of various body areas, including the abdomen, flanks, thighs, submental and submandibular areas, back fat, bra fat, and banana roll. It has been clinically proven to reduce fat bulges, allowing patients to achieve noticeable and measurable aesthetic results without the pain, expense, downtime, and risks associated with existing invasive and minimally-invasive procedures.

Clinical studies of the CoolSculpting System used on the abdomen have demonstrated the treatment to be safe and effective for the reduction of subcutaneous fat. Subjects in a recent study rated their satisfaction with the CoolSculpting procedure at 73% and 89% indicated they would recommend the procedure. ^[1]

While the CoolSculpting procedure is successful in reducing subcutaneous fat in the abdomen, ZELTIQ Aesthetics is exploring the concept of combining other non-invasive aesthetic treatment modalities to enhance and/or improve the contouring effects of CoolSculpting.

ZELTIQ P/N: [REDACTED]
Protocol Number: ZAT8-003

[REDACTED]

Electromagnetic muscle stimulation (EMS), also known as neuromuscular electrical stimulation (NMES) is the elicitation of muscle contraction using electric impulses. The impulses mimic the action potential that comes from the central nervous system, causing the muscles to contract. ^[2]

EMS devices are frequently used in physical therapy or rehabilitation settings to strengthen and tone muscles damaged by illness or disease but they may also be used for other purposes. ^[3] High intensity EMS devices can elicit stronger, more effective muscle contractions believed to increase muscle strength and endurance. EMS has received an increasing amount of attention in the last few years from fitness enthusiasts as various manufacturers promote the technology for muscle strengthening, firming and improvement in muscle tone specifically in the abdomen, buttocks and thighs. ^[4]

[REDACTED]

1.2 *Device Descriptions*

EMS Devices

Electromagnetic (EMS) devices that may be used in this evaluation produce electromagnetic muscle stimulation by a non-contact magnetic field in tissue. Each device under consideration for use in this study has the same indications for use and similar technological characteristics and principles of operation. Figure 1 below depicts a representative EMS device.

[figure not shown]

Figure 1. Representative EMS Device

ZELTIQ P/N: [REDACTED]
Protocol Number: ZAT8-003

[figure not shown]

All EMS devices considered for use in the proposed evaluation have the following indications:

- Improvement of abdominal tone, strengthening of the abdominal muscles, development of firmer abdomen.

EMS devices utilized in this study will be operated in accordance with the manufacturer's Instructions for Use.

CoolSculpting System

[figure not shown]

Both the control unit and the applicators are cleared by the FDA and are commercially available.

Safety features are built into the device to avoid any unexpected excursions in temperature. The device will automatically shut down if the thermal exposure at the skin interface exceeds specified criteria.

[figure not shown]

Figure 2: ZELTIQ CoolSculpting System control unit.

ZELTIQ P/N: [REDACTED]
Protocol Number: ZAT8-003

This document and the contents hereof are considered proprietary and confidential information of ZELTIQ Aesthetics, Inc. Disclosure to unauthorized individuals or dissemination, publication or copying is prohibited without prior written consent of ZELTIQ.

The materials used for patient-contacting surfaces are all common materials with a history of use in medical and/or skin-contact consumer applications or have been tested for biocompatibility.

1.3 Regulatory Status

The EMS devices that may be used in the proposed evaluation are non-significant risk devices. [REDACTED] Other devices under consideration for use in this study may not be FDA cleared, and will have similar technological characteristics and principles of operation, and have passed all performance and safety testing.

The ZELTIQ CoolSculpting System received market clearance on August 24, 2010 for “use as a non-invasive dermatological aesthetic treatment to affect the appearance of flanks” (DEN090002). On May 9, 2012, the ZELTIQ System received market clearance for treatment of the abdomen (K120023); on April 9, 2014 the System received market clearance for treatment of the thighs (K133212); and on September 24, 2015 the System received market clearance for treatment of the submental area (K151179). Subsequently, the System received clearance for bra fat, back fat and banana roll (K160259), upper arms (K162050), the submandibular area (K181740), and can affect the appearance of lax tissue after submental treatment (K172144). [REDACTED]

The device was also previously cleared for cooling as a method to minimize localized pain and thermal injury during laser and dermatological treatments under: K060407 (initial clearance), K063715 (clearance for warming and massage), K072152 (clearance for flat and belt applicators), K080118 (clearance for vacuum applicator), and K090094 (clearance for commercial device).

ZELTIQ P/N: [REDACTED]
Protocol Number: ZAT8-003

2. Study Protocol

2.1 Design

Prospective, multi-center, non-randomized, feasibility study

2.2 Study Duration

Enrollment and follow-up is expected to take up to six (6) months for each subject.

2.3 Physician Participants

Study Investigators must be practicing medical physicians with experience in the use of the CoolSculpting System and EMS devices.

2.4 Site Requirements

Site Investigators must have at least one study coordinator with experience in conducting aesthetic research and with sufficient time to perform study activities.

2.5 Subject Recruitment

Patients who seek reduction of fat layer in the abdomen, and/or who wish to have adjunctive treatment for abdominal firming and toning will be recruited for this study.

2.6 Sample Size

A maximum of sixty (60) subjects will be included in the study.

- l) Subject has any dermatological conditions, such as moderate to excessive skin laxity, or scars in the location of the treatment sites, that may interfere with the treatment or evaluation (stretch marks is not an exclusion).
- m) Subject has a metal implant or active implanted device such as a pacemaker, defibrillator, or drug delivery system.
- n) Subject has been involved in any type of abdominal muscle training program within the previous 6 months.
- o) Subject has pulmonary insufficiency.
- p) Subject has a cardiac disorder.

ZELTIQ P/N: [REDACTED]
Protocol Number: ZA18-003

- q) Subject has a malignant tumor.
- r) Subject has been diagnosed with epilepsy.
- s) Subject currently has a fever.
- t) Subject is pregnant or intending to become pregnant during the study period (in the next 9 months).
- u) Subject is lactating or has been lactating in the past 6 months.
- v) Subject is unable or unwilling to comply with the study requirements.
- w) Subject is currently enrolled in a clinical study of any other investigational drug or device.
- x) Any other condition or laboratory value that would, in the professional opinion of the Investigator, potentially affect the subject's response or the integrity of the data or would pose an unacceptable risk to the subject.

2.8 ***Informed Consent***

Study candidates shall receive an explanation of the study objectives, possible risks and benefits of the study, and be given adequate time to read the information included in the informed consent document. Candidates will be given an opportunity to ask questions about any of the information contained in the informed consent. Candidates must verbally acknowledge understanding of the informed consent, and sign the consent form accordingly. This form must have prior approval of the Institutional Review Board (IRB).

2.9 ***Screening Procedures***

Once informed consent is obtained, interested subjects will undergo screening.

Screening Visit; Required; Day -60 to Day 0

After the informed consent is signed, subjects will be screened for eligibility.

Each subject will be evaluated to determine that all selection criteria are met.

The Investigator or designee shall complete a brief medical history and examine the subject to confirm eligibility for the study.

1. Obtain height and weight.
2. Calculate BMI
3. Assess for any medical conditions that would lead to exclusion of a subject from the study.
4. Document potential candidate's medication use (including over-the-counter medications, vitamins, and herbs), Fitzpatrick Skin Type, and ethnicity as

ZELTIQ P/N: [REDACTED]
Protocol Number: ZAT8-003

well as any skin irregularities (e.g. moles, birth marks, scars, stretch marks, discoloration) at the intended treatment area.

5. All female subjects of childbearing potential will be asked to take a pregnancy test (urine) prior to being treated. If the subject is pregnant, she will be excluded from participation.

Female subjects of childbearing potential will be advised to avoid becoming pregnant during the course of the study by using a medically accepted form of contraception if they are sexually active. If the subject becomes pregnant during the course of the study, she will not be treated subsequently with the study device or be required to have follow-up photographs taken or any other efficacy assessment performed.

All subjects will be asked to maintain their weight by not making any major changes to their diet or exercise regimen during the course of the study. Subjects who do not maintain their weight within 5% will still continue in the study. However, if the weight change is more than 5% after the final treatment, the subjects' data will be excluded from the per protocol data analysis. All subjects will be asked to avoid sun tanning during the course of the study.

After completion of the screening procedures and confirmation of eligibility, subjects will be assigned to one of four treatment groups described in **Table 2** below.

Table 2. Treatment Cohorts

Cohort 1	Cohort 2	Cohort 3	Cohort 4
EMS only (4 sessions)	EMS (4 sessions) followed by CoolSculpting (3-6 cycles)	CoolSculpting only (3-6 cycles)	CoolSculpting (3-6 cycles) followed by EMS (4 sessions)

Subjects that do not meet all eligibility criteria will be excluded from further participation in the study.

2.10 Enrollment

Study candidates who sign the informed consent form, meet eligibility criteria, and undergo initiation of study treatment are considered enrolled. Study treatment initiation is defined as the initiation of treatment with a study device after the placement of the applicator on the intended treatment area on the scheduled treatment day.

2.11 Photo Visit; Required, day -30 to 0

All subjects will have their photos taken within 30 days prior to study treatment.

- a) Obtain weight.
- b) Obtain baseline 3-Dimensional photographs of the abdomen using Vectra or similar imaging system.
- c) Obtain baseline photographs of the treatment area using standardized setup and settings.

2.12 Study Treatment

Treatment Visit 1; Required; Day 0

Treatment instructions for the four (4) interventional cohorts are described below:

2.12.1 COHORT 1

For subjects assigned to receive EMS as a stand-alone intervention (**Cohort 1**), preparation activities are described in steps 2.12.1 a) through k):

- a) Review inclusion and exclusion criteria.
- b) Repeat pregnancy test for female subjects of childbearing potential (urine). Exclude subject from participation if the results are positive.
- c) If the subjects meet all of the inclusion criteria and none of the exclusion criteria, then proceed with the study treatment.
- d) Obtain weight prior to first EMS treatment.
- e) Apply EMS device per manufacturer's Instructions for Use, and place one or two applicators in the center of treatment area.
- f) Support the EMS device with treatment arm, pillows or straps as needed.

ZELTIQ P/N: [REDACTED]
Protocol Number: ZAT8-003

- g) Initiate treatment using recommended program for abdominal toning and firming supplied by manufacturer.
- h) Record the highest % energy utilized for the EMS treatment.
- i) At the conclusion of the EMS treatment, the site(s) will be examined for any epidermal, dermal, or subcutaneous findings (e.g., blanching, erythema, bruising, swelling); alterations in sensation (e.g., numbness, tingling).
- j) [REDACTED]
- k) Three (3) additional EMS treatment visits will be scheduled wherein the intervention will be repeated for a total of 4 treatment sessions to occur within a two-week period. Treatment Visits 2, 3 and 4 will be performed as specified in **Section 2.12.1 a) through j)**.

2.12.2 COHORT 2

For subjects assigned to receive EMS treatments prior to CoolSculpting (**Cohort 2**), follow steps in **Section 2.12.2 a) through k)**:

- a) Review inclusion and exclusion criteria.
- b) Repeat pregnancy test for female subjects of childbearing potential (urine). Exclude subject from participation if the results are positive.
- c) If the subjects meet all of the inclusion criteria and none of the exclusion criteria, then proceed with the study treatment.
- d) Obtain weight prior to first EMS treatment.
- e) Apply EMS device per manufacturer's Instructions for Use, and place one or two applicators in the center of the treatment area.
- f) Support the EMS device with treatment arm, pillows or straps as needed.
- g) Initiate treatment using recommended program for abdominal toning and firming supplied by manufacturer.
- h) Record the highest % energy utilized for the EMS treatment.
- i) At the conclusion of the EMS treatment, the site(s) will be examined for any epidermal, dermal, or subcutaneous findings (e.g., blanching, erythema, bruising, swelling); alterations in sensation (e.g., numbness, tingling).
- j) [REDACTED]

k) Three (3) additional EMS treatment visits will be scheduled wherein the intervention will be repeated for a total of 4 treatment sessions to occur within a two-week period. Treatment Visits 2, 3 and 4 will be performed as specified in Section 2.12.2 a) through j).

l) At the conclusion of the 4th EMS treatment or within 7 days, the subject will receive multiple CoolSculpting cycles per the Investigator's discretion. Cooling cycles may be applied to the upper or lower abdomen or in both areas. CoolSculpting treatments will be performed using a minimum of 3 cycles and will not exceed 6 cycles. Per Investigator discretion, CoolSculpting cycles may be performed simultaneously (dual-sculpting method).

i. Obtain subject's weight.
[REDACTED]

[REDACTED]

[REDACTED]

[REDACTED]

[REDACTED]

[REDACTED]

[REDACTED]

x. Immediately post treatment, the treatment site will be examined for any epidermal, dermal or subcutaneous findings (e.g., blanching, erythema, bruising, swelling), and alterations in sensation (e.g., numbness, tingling).

xi. [REDACTED]

xii. [REDACTED]

ZELTIQ P/N: [REDACTED]
Protocol Number: ZAT8-003

2.12.3 COHORT 3

For subjects assigned to **Cohort 3**, all CoolSculpting cycles will be completed in a single visit.

- a) Review inclusion and exclusion criteria.
- b) Repeat pregnancy test for female subjects of childbearing potential (urine).
Exclude subject from participation if the results are positive.
- c) If the subjects meet all of the inclusion criteria and none of the exclusion criteria, then proceed with the study treatment.
- d) Obtain weight.
- e) Use template to mark the treatment areas on the abdomen.
- f) Apply a new gasket onto applicator, then, attach the contour.

[REDACTED]

- n) Immediately post treatment, the treatment site will be examined for any epidermal, dermal or subcutaneous findings (e.g., blanching, erythema, bruising, swelling), and alterations in sensation (e.g., numbness, tingling).
- o) [REDACTED]

The need for post-treatment care is not expected for this study. Subjects will be encouraged to call the study site if they experience any unusual effects (e.g., severe discomfort, severe and/or prolonged erythema, bruising, swelling; blistering, etc.), which may be related to the study.

2.12.4 COHORT 4

For subjects assigned to **Cohort 4**, all CoolSculpting cycles will be completed in a single visit as part of prior participation in Cohort 3 of this protocol. For these subjects assigned to receive EMS treatments, follow steps **in Section 2.12.4 a) through k)**:

- a) Review inclusion and exclusion criteria.
- b) Repeat pregnancy test for female subjects of childbearing potential (urine). Exclude subject from participation if the results are positive.
- c) If the subjects meet all of the inclusion criteria and none of the exclusion criteria, then proceed with the study treatment.
- d) Obtain weight prior to first EMS treatment.
- e) Apply EMS device per manufacturer's Instructions for Use, and place one or two applicators in the center of the treatment area.
- f) Support the EMS device with treatment arm, pillows or straps as needed.
- g) Initiate treatment using recommended program for abdominal toning and firming supplied by manufacturer.
- h) Record the highest % energy utilized for the EMS treatment.
- i) At the conclusion of the EMS treatment, the site(s) will be examined for any epidermal, dermal, or subcutaneous findings (e.g., blanching, erythema, bruising, swelling); alterations in sensation (e.g., numbness, tingling).
- [REDACTED]
- k) Three (3) additional EMS treatment visits will be scheduled wherein the intervention will be repeated for a total of 4 treatment sessions to occur within a two-week period. Treatment Visits 2, 3 and 4 will be performed as specified in **Section 2.12.4 a) through j)**.

2.12.5 Additional EMS Treatment Visits; Required

EMS Treatment Visit 2 (Cohorts 1, 2 and 4); Required; during Week 1 following first EMS treatment

- a) Review and verify the subject continues to meet all eligibility criteria.

ZELTIQ P/N: [REDACTED]
Protocol Number: ZAT8-003

This document and the contents hereof are considered proprietary and confidential information of ZELTIQ Aesthetics, Inc. Disclosure to unauthorized individuals or dissemination, publication or copying is prohibited without prior written consent of ZELTIQ.

- b) Repeat pregnancy test for female subjects of childbearing potential (urine).
Exclude subject from participation if the results are positive.
- c) Perform EMS treatment as described in **Section 2.12.1 a) through j).**

EMS Treatment Visit 3 (Cohorts 1, 2 and 4); Required; during Week 2 following first EMS treatment

- a) Review and verify the subject continues to meet all eligibility criteria.
- b) Repeat pregnancy test for female subjects of childbearing potential (urine).
Exclude subject from participation if the results are positive.
- c) Perform EMS treatment as described in **Section 2.12.1 a) through j).**

EMS Treatment Visit 4 (Cohorts 1, 2 and 4); Required; during Week 2 following first EMS treatment

- a) Review and verify the subject continues to meet all eligibility criteria.
- b) Repeat pregnancy test for female subjects of childbearing potential (urine).
Exclude subject from participation if the results are positive.
- c) Perform EMS treatment as described in **Section 2.12.1 a) through j).**
- d) Obtain 3-Dimensional photographs of the abdomen using Vectra or similar imaging system.
- e) Obtain photographs of the treatment area using standardized setup and settings (Optional). See Section 2.14 for details.

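### At EMS Visits 2 to 4, a positive pregnancy test excludes an already treated subject from participation, which read literally conflicts with the follow-up rules in 2.9 and 2.13

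*Combined protocol and SAP*

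**What the plan says.** Section 2.12.5 b) requires a urine pregnancy test at EMS Visits 2, 3 and 4 in Cohorts 1, 2 and 4, with the instruction "Exclude subject from participation if the results are positive". The same instruction is step b) of 2.12.1, 2.12.2 and 2.12.4. It is invoked again at the later visits, both by step c) of 2.12.5 and by step k) of each cohort section; for Cohort 2 this reads "Treatment Visits 2, 3 and 4 will be performed as specified in Section 2.12.2 a) through j".

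Four other places bear on the same subject:

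- **2.10** fixes when a subject is in the study: "Study candidates who sign the informed consent form, meet eligibility criteria, and undergo initiation of study treatment are considered enrolled".
- **2.9** has two pregnancy rules. For a positive test at screening: "If the subject is pregnant, she will be excluded from participation". For a pregnancy that arises later in the trial: "she will not be treated subsequently with the study device or be required to have follow-up photographs taken or any other efficacy assessment performed".
- **2.13** requires subjects who have received study treatment to complete the 2-, 4- and 12-week follow-up. It makes no exception for pregnancy.
- **2.18** has AEs assessed throughout the study and collected until the follow-up visit.

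**The concern.** An instruction suited to a candidate who has not been treated is carried unchanged to visits where the subject has already been treated. At screening, the phrase means that the woman leaves the study. A coordinator who meets the same phrase at Visit 2 has a reason within the protocol to read it the same way.

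On that reading, a device-exposed pregnant subject would lose her scheduled AE contacts. Those contacts supply the UADE endpoint and the percentage of subjects with each AE term (2.16.3). Section 2.18 also counts fetal distress, fetal death and congenital abnormality as serious events, so this is a subject whose scheduled safety contacts should not lapse through a wording accident.

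**Working it through.** **1. The instructions side by side, for a woman who tests positive at EMS Visit 2, 3 or 4**

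| Place | Device treatment | Photographs and efficacy | AE follow-up |
|---|---|---|---|
| 2.12.5 b), read literally | stops | stops | stops |
| 2.9, pregnancy during study | stops | not required | not waived, but not stated to continue |
| 2.13 | silent | required | required |
| 2.18 | silent | silent | continues to the follow-up visit |

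The last column holds the conflict. A smaller one sits in the middle: 2.13 requires all assessments, while 2.9 waives some.

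**2. Is the sentence needed to stop treatment?** No. Pregnancy is exclusion criterion t) in 2.7, and step c) of the cohort sections says "If the subjects meet all of the inclusion criteria and none of the exclusion criteria, then proceed with the study treatment". A positive test blocks the session without the sentence in step b). At these visits the sentence adds only the doubt about follow-up.

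**3. Which contacts are at stake?** Days counted from the last treatment received (2.13.1 to 2.13.3):

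- 2-week contact: 14 ± 3 = Days 11 to 17
- 4-week visit: 28 ± 7 = Days 21 to 35
- 12-week visit: 84 ± 14 = Days 70 to 98

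Now convert to study days from the first EMS session. Assume Week 1 is Days 1 to 7, Week 2 is Days 8 to 14, and Visit 3 falls on an earlier day than Visit 4. The last session received is then Day 0, Days 1 to 7, or Days 8 to 13.

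| Positive at | 2-week | 4-week | 12-week | Shortest time from test to close of 2-week window |
|---|---|---|---|---|
| Visit 2 | 11–17 | 21–35 | 70–98 | 0 + 17 − 7 = 10 days |
| Visit 3 | 12–24 | 22–42 | 71–105 | 1 + 17 − 13 = 5 days |
| Visit 4 | 19–30 | 29–48 | 78–111 | 8 + 17 − 14 = 11 days |

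None of the three windows has closed at the time of the test, so all three contacts could be lost.

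**4. What would those contacts detect?** Section 6.2 defines four AE terms by duration: erythema over 2 weeks, bruising and swelling over 1 month, and sensory change over 12 weeks. An EMS-related event can have lasted at most 14 days by Day 14, so none of the four can yet have been met. One limit applies: a sensory change that begins at the last treatment passes 12 weeks only after Day 84. A 12-week visit held between Days 70 and 84 could not confirm it.

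**5. How many subjects?** The documents give neither a pregnancy rate nor the number of women of childbearing potential, so both are assumed. Expected cases = n × yearly rate × 14/365:

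- 15 × 0.01 × 14/365 = 0.006
- 60 × 0.01 × 14/365 = 0.023
- 15 × 0.10 × 14/365 = 0.058
- 60 × 0.10 × 14/365 = 0.230

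The top figure requires all 60 subjects to be women of childbearing potential who receive EMS. Men and subjects up to age 65 are eligible, so it is an upper bound for that rate.

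**6. Effect on the safety estimate.** The plan specifies no interval for UADEs. For scale only, the exact two-sided 95% upper limit with no events is 1 − 0.025^(1/n): 5.96% with 60 subjects and 6.06% with 59. One case would be 1/60 = 1.7% of the maximum enrolment.

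**The case against.** The strongest reply is that the protocol already answers the question. A woman at Visits 2 to 4 is enrolled, so the 2.9 rule for pregnancy during the study covers her, and that rule waives no safety assessment. Section 2.13 keeps treated subjects in follow-up, and 2.18 collects AEs until the follow-up visit. The disputed step stands just before the instruction to treat, so it can be read simply as a bar on that session.

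Safety capture would not vanish either. Table 3 schedules an AE assessment at each EMS visit, including the one with the positive test. Section 2.12.3 encourages subjects to call about unusual effects. SAEs and UADEs are reportable within 24 hours of knowledge. Bruising, swelling and sensory change are listed in 6.2 as anticipated effects of CoolSculpting, not EMS, although the examination after each EMS session does look for them.

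Most of this stands, and it sets the severity. A reader might infer that the protocol orders sites to abandon pregnant exposed subjects. Taken as a whole, it does not. A reader might also infer that the safety or efficacy results would be distorted. Step 6 shows how little one subject moves the safety limit, and 2.16.2 already leaves subjects who do not complete treatment out of the efficacy analyses.

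What the reply does not remove is the conflict itself. Section 2.9 never says outright that AE follow-up continues, and nothing limits the sentence at Visits 2 to 4 to withholding treatment. A site must infer the intended rule against an explicit instruction.

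**Conclusion.** The concern holds as a low-severity conflict between stated instructions. Loss of the three AE contacts is possible, not certain, and depends on how a site reads the step. Well under one case is expected on the assumptions in step 5, and the effect on any estimate is negligible. The reason to correct it is the safety of a device-exposed pregnant subject.

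The point extends to one group before its first EMS session. Cohort 4 women received CoolSculpting in Cohort 3 up to 6 months earlier (2.7 criterion g; 2.12.4), so step b) at their EMS Visit 1 also reaches subjects with prior study treatment. For Cohorts 1, 2 and 3, the present wording before first treatment is appropriate.

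**What to change.** In 2.12.5 b) for Visits 2, 3 and 4, and in 2.12.4 b) for Cohort 4 at EMS Visit 1, replace the sentence with:

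> If positive, give no further study device treatment; photographs and efficacy assessments are not required (2.9); continue the scheduled 2-, 4- and 12-week AE follow-up (2.13, 2.18), timed from the last study treatment received.

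State that this replaces step b) of 2.12.1, 2.12.2 and 2.12.4 when that step is invoked again at Visits 2 to 4. Add a cross-reference in 2.13 to the exception in 2.9. Keep the present wording at Visit 1 for subjects with no prior study treatment.

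Timing from the last treatment received is needed because the planned final treatment will not take place. For a Cohort 4 woman who tests positive at EMS Visit 1, the clock runs from CoolSculpting, so only contacts still outstanding apply.

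The cost is one sentence used in four places, one statement of precedence and one cross-reference. No visit, procedure or form is added, and the bar on treating a pregnant subject is unchanged.
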